PART B STUDY DESCRIPTION

TITLE OF PROTOCOL	EEG changes with meditation: A proposal to analyze EEG changes with a simple, online, guided meditative tool
Principal Investigator	[name] [name]

B1. PURPOSE OF PROTOCOL

The purpose of this study is to assess:

- a) the qualitative EEG measures associated with meditation
- b) the observed difference in EEG changes between novice and experienced meditators
- c) the observed difference in EEG changes between the start and end of 6 weeks of daily meditation

[figure not shown]
B2. SIGNIFICANCE AND BACKGROUND FOR THE STUDY

Meditation refers to a category of self-regulation practices which focus on training attention and awareness in order to bring mental processes under greater voluntary control. Meditation, as therapy, has the potential to improve mental well-being and development in specific capacities such as calmness, clarity, and concentration.¹ Mindfulness is defined in psychological terms as being characterized by paying total attention to the present moment with a nonjudgmental awareness of inner and outer experiences.²

Meditation and current literature:

Studies have shown numerous benefits of meditation techniques. For example, Goyal et al. reported that meditation has a similar effect on anxiety and depression as compared to medication without the side effects.³ Therefore, it is essential to assess the usefulness of incorporating meditation as an adjunctive therapy in perioperative patient care.

In order to study the benefits and efficacy of meditation intervention, it is important to have an objective measure that assesses the quality of meditation. Ahani et al. reported that EEG signals are sensitive to meditation using coherence and synchrony techniques as well as spectral analysis.⁴ The overall effect of meditation is decreased electro-cortical arousal.⁵ Meditators have shown to have higher alpha and theta activities in EEGs than non-meditators.⁶ Focused-attention has shown to produce an increase of gamma activity in the brain.⁷ Studies have also shown that meditation produces different activities at different locations such as increased alpha activity in frontal regions⁸ and posterior regions.⁹

EEG spectral analysis of alpha, beta, and theta waves during meditation. Credits :Ahani et al¹⁰

[figure not shown]

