A meta-analysis conducted in 2014 showed the most consistently altered brain regions were the left rostral medial prefrontal cortex, anterior/mid cingulate cortex, anterior insula, primary/secondary somatomotor cortices inferior temporal gyrus, and hippocampus.¹¹ Insula is consistently linked to interoception-awareness of the body's internal and visceral states, including respiration, heart rate, emotional self-awareness, and potentially metacognitive awareness.^{12,13} Somatosensory areas are also altered by meditation.

Neuroimaging studies have shown that there is increased cortical thickening in the left prefrontal lobe cluster as well as increased volume of insula, right temporal, and right angular gyrus.¹⁴ Meditators have also shown to have increased grey matter volume.

Central box represents the value from the lower to upper quartile (25th to 75th percentile). The middle line represents the median. The vertical line extends from the minimum to the maximum value.¹⁴

Experienced and novice meditators:

A recent study has shown that after practicing 5-60 hours of meditation, novice meditators experience structural differences in 7 grey matter and 5 white matter tract regions.¹⁵

Number	Grey Matter areas	White matter areas
1)	Anterior cingulate cortices	Corpus callosum
2)	Posterior cingulate cortices	Superior longitudinal fasciculus
3)	Insular cortex	Sagittal stratum
4)	Temporoparietal junction	Thalamic radiation
5)	Hippocampus	Corona radiata.
6)	Caudate nucleus	
7)	Cerebellum	

A recently published study reports that meditation resulted in effortless awareness in novice and experienced meditators and meditation was associated with lower activity in Posterior Cingulate Cortices (PCC).¹⁵ A recent study has shown that meditation correlates with decreased activity of default mode network¹⁶ as opposed to an increased activity of default mode network associated with mind wandering and self-referential processes.¹⁷

Network integration

A recent study has also assessed the network integration in EEG due to meditation and has found that meditation is associated with increased brain network integration.¹⁵ Such studies demonstrate the possibility of application of real time EEG to associate an objective measure of brain activity with subjective mind states related to meditation. EEG has an excellent temporal resolution and is preferred over fMRI in this study since it is portable and less expensive.

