Meditation encompasses a family of complex practices that include yoga meditation, mindfulness meditation, mantra meditation, tai chi, etc. However, the training requirements for these types of meditation are variable including training from a trained teacher. Isha Kriya is a type of meditation that does not involve complicated trainings, rituals or mantras and can be performed anywhere at any time. Isha Kriya is a meditation technique that regulates breathing and produces a positive effect on the mind and body as endorsed by millions of people worldwide.¹⁸ At this time, no studies have been done regarding the EEG changes in the brain during Isha Kriya.

This study will investigate if Isha Kriya produces EEG changes comparable to that of established literature and will look at the differences between the start and the end of a 6 week cycle. This study will also explore the difference in EEG changes between experienced and novice meditators.

B3. DESCRIPTION OF RESEARCH PROTOCOL

A. Study Design – Overview, Methods, Procedures

Study design:

This is a prospective trial enrolling healthy volunteers, including novice meditators and experienced meditators. Subjects will undergo an EEG at baseline and again after 6 weeks. During the 6 weeks, subjects will be asked to meditate twice a day, 12 minutes each time.

Recruitment:

Recruitment will occur via flyers posted at BIDMC and flyers emailed to mediation listservs.

Study procedures:

1) EEG

Subjects will undergo an EEG at baseline and again after 6 weeks (+/- 1 week). During the EEGs, the subjects will be asked to meditate.

The ENOBIO 32 EEG device is an investigational device under US federal law which is a 24-bit EEG data reader at the rate of 500 S/s which comes as a wearable wireless electrophysiology sensor system. It includes spectrogram and 3D visualization in real time of spectral features. It also collects triaxial accelerometer data. These data are stored in microSD offline in Holter mode.¹⁹ This EEG communicates via wireless allowing the subjects to be in a comfortable position and also can reduce the effects of electrical interference. EEG measures brain waves by the following processes:

Pre-processing Signal

Down sampling will be done to eliminate interference from unexpected signals.

After down sampling, Band Pass Filter (BPF) will be used to filter the signals.

Ensemble Average

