In this step, signal acquired from every selected channel would be averaged. There are fifteen signals from the instruction that are averaged into one signal representing the instruction.

Short Time Fourier Transform (STFT)

STFT will be used to determine a dominant frequency from the signal of an ensemble average result when the event occurs.

Event Related Desynchronization/Event Related Synchronization

ERD/ERS during event is calculated with the above data.

2) Meditation

Subjects will be introduced to Isha Kriya (IK) meditation. IK is a meditation that can be learned quickly and requires approximately 12 minutes, twice a day of practice. This regimen was chosen because of its simplicity making it an excellent way to introduce meditation to beginners. IK does not incorporate a spiritual or religious focus. [name], the principal investigator of the study, was trained to be an instructor by the Isha Institute of Inner Sciences, a nonprofit foundation located at McMinnville, Tennessee.

At the time of enrollment, [name], or a trained research team member, will provide a brief introduction to IK meditation and review a handout of the meditation instructions. The subjects can utilize the online-guided meditation or follow the instructions on their own.

Preparation: Sit in a cross-legged posture or sit in a chair, spine comfortably erect, hands upon thighs, palms facing up, face slightly upturned, eyes closed, keeping a mild focus between the eyebrows.

Meditation: Slow inhaling and exhaling while mentally focusing on the words "I am not the body" and "I am not even the mind" for 7 minutes; uttering a long "Ahh" sound seven times; sitting for 5 minutes with eyes closed.

Subjects will be asked to practice the meditation twice daily for 12 minutes each session, for approximately 6 weeks. They will be given a meditation diary to complete daily.

	Baseline	After 6 weeks
Group 1 - Novice meditators	Meditation with EEG monitoring	Meditation with EEG monitoring
Group 2 - Experienced meditators	Meditation with EEG monitoring	Meditation with EEG monitoring

Study Monitoring / Adverse Events:

The study interventions are non-invasive and minimal risk. Therefore, we will limit the scope of AE monitoring and reporting to the following:

- All Serious Adverse Events believed to be related to the study procedures
- Unexpected, non-serious Adverse Events believed to be related to the study procedures

B. Statistical Considerations

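### Nothing in the plan separates awake, on-technique EEG time from drowsy or off-task time, so a difference in drowsiness could be read as an experience or 6-week effect

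*Combined protocol and SAP*

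**What the plan says.** B3.A, 1) EEG gives a single instruction for both recordings: "During the EEGs, the subjects will be asked to meditate". The group-by-visit table in B3.A, 2) Meditation shows one condition in all four cells, "Meditation with EEG monitoring".

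The technique is described in the same subsection. The posture is "face slightly upturned, eyes closed, keeping a mild focus between the eyebrows". The session is 7 minutes of slow breathing with two mental phrases, then seven audible utterances, then "sitting for 5 minutes with eyes closed".

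The listed signal steps are down-sampling, band-pass filtering, channel averaging, a short-time Fourier transform, and event-related desynchronization/synchronization (ERD/ERS). The last two are tied to an event that is not defined.

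B2 states the expected pattern: "The overall effect of meditation is decreased electro-cortical arousal", and "Meditators have shown to have higher alpha and theta activities in EEGs than non-meditators". It also cites more gamma with focused attention. The end of B2 says Isha Kriya will be compared with that established literature. The network-integration paragraph of B2 presents EEG as a way to "associate an objective measure of brain activity with subjective mind states related to meditation".

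B3.B makes power spectral density part of the primary endpoint, names alpha against beta as the EEG change to be noted, and lists novice versus experienced and start versus end of 6 weeks as secondary endpoints.

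**The concern.** The study wants to attribute EEG features to meditation, but it records nothing that shows whether the subject was awake and using the technique at the time. Quiet sitting with eyes closed invites drowsiness, and drowsiness is itself a low-arousal state. Observing lower arousal or more theta therefore does not show that meditation produced it.

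The two secondary contrasts are exposed as well. A novice who has just been introduced to the technique and someone who meditates at least 30 minutes a day may differ in how readily they doze, and one subject may differ between visits. The analysis set may be as small as 10 completers across both groups, so a few drowsy recordings could move a group summary. A self-report not taken at the session cannot be recovered later.

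**Working it through.** **Step 1. Is there any check in the documents?**

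- *Instruction:* subjects are asked to meditate; no compliance or wakefulness check is attached (B3.A, 1) EEG).
- *Signal processing:* no step rejects or labels drowsy, sleep-onset or off-task epochs (B3.A, 1) EEG).
- *Diary:* completed daily and described with the six weeks of home practice; not described as a report on the EEG session (B3.A, 2) Meditation).
- *Accelerometer:* recorded by the device, with no stated analysis use (B3.A, 1) EEG).
- *Utterances:* overt behaviour in mid-session, but not used as a check, and they come before the silent period (B3.A, 2) Meditation).
- *Exclusion criteria:* neither sleep disorders nor sedative use appears (B3.C).

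No check exists. The part of the session with no observable task at the end is 5 / 12 = 42%.

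**Step 2. Which way would drowsiness push the endpoints?** The documents do not discuss drowsiness. The directions below are assumptions from general EEG knowledge.

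- *Arousal:* B2 expects lower; drowsiness lowers it. Same direction, so it mimics.
- *Theta:* B2 expects higher; drowsiness is assumed to raise it. Same direction, so it mimics.
- *Alpha:* B2 expects higher; drowsiness is assumed to lower it. Opposite direction, so it masks, and it distorts alpha against beta.

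**Step 3. How large could it be?** The plan gives no figure to reproduce on this point. Its only sample-size figures (at least 10 completers, 15 recruited) come with no effect size or standard deviation. For illustration, let f be the drowsy share of the analysed time, k the drowsy-to-waking theta power ratio (assumed 1.5 to 3), and a the drowsy-to-waking alpha power ratio (assumed 0.3 to 0.5).

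Apparent theta ratio = 1 + f(k − 1):

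- f = 10%: 1 + 0.1 × 0.5 = 1.05 to 1 + 0.1 × 2 = 1.20
- f = 30%: 1 + 0.3 × 0.5 = 1.15 to 1 + 0.3 × 2 = 1.60

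Apparent alpha ratio = 1 − f(1 − a):

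- f = 10%, a = 0.5: 1 − 0.1 × 0.5 = 0.95
- f = 30%, a = 0.3: 1 − 0.3 × 0.7 = 0.79

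Contrast between two groups or visits with 30% and 10% drowsy time, and no true difference:

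- Theta, k = 1.5: 1.15 / 1.05 = 1.10
- Theta, k = 2: 1.30 / 1.10 = 1.18
- Theta, k = 3: 1.60 / 1.20 = 1.33

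The same 20-point gap gives 1.10 to 1.40 only if the comparison side has no drowsy time at all (20% against 0%).

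**The case against.** Several counter-arguments carry weight.

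- **Whole recording.** A reader might infer that the entire recording is treated as meditation. The documents do not say so. The Fourier and ERD/ERS steps refer to an event, and although that event is undefined, they are not described as a whole-record average. What can be said is that no rule separates one kind of time from the other. The arithmetic above applies to whatever time is averaged.
- **Whole signature.** A reader might infer that drowsiness would reproduce the full expected pattern. It would not. B2 expects higher alpha and cites gamma, and the only band contrast named in B3.B is alpha against beta. The overlap is limited to arousal and theta; for alpha the risk is masking.
- **Unequal dozing.** Nothing in the documents shows that drowsy time differs by group or visit. This is a possibility that the study could not rule out, not a demonstrated bias.
- **The session is not all passive.** Seven minutes carry a set mental task, the spine is erect, and the utterances are audible. This lowers the risk but leaves the silent 5 minutes uncovered.
- **Pilot status.** The study is small and descriptive, and the stored recordings could be reviewed later. It also has no resting condition, so attribution to meditation is limited even in fully awake subjects. All of this stands and keeps the point modest. However, self-reports are lost if not collected, a flagging rule written after the data are seen is less credible, and B3.B still applies a two-sided 0.05 threshold.
- **Selecting on the outcome.** Dropping epochs for alpha loss and making the remainder the main analysis would mechanically raise alpha, which is one of the expected findings. This objection is correct and shapes the fix.

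**Conclusion.** The plan has no measure or rule that distinguishes awake, on-technique time from drowsy or off-task time at either EEG. Drowsiness can mimic the lower arousal and higher theta that B2 expects, and can hide the expected alpha rise. A difference in drowsy time could therefore be mistaken for a difference between novices and experienced meditators or for a 6-week change.

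The size is unknown. The spurious theta ratio of about 1.10 to 1.33 rests on assumed drowsy shares of 30% and 10% and on drowsy theta at 1.5 to 3 times waking; none of these comes from the documents. The absence of a check does not depend on those values. The effect is on interpretation, not on a power or error-rate figure. A cheap improvement is worth making before data are collected.

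**What to change.** 1. After each EEG, collect two fixed 0–10 items (sleepiness during the session; share of the session spent on the technique) and a yes/no question on whether the subject fell asleep. Report them by group and visit.
2. Before the data are seen, write a sleep-onset flagging rule that does not rest on alpha loss alone: for example vertex waves or spindles, or slow eye movements where the frontal channels allow.
3. Keep the all-epoch summaries as the main analysis, report the flagged share by group and visit, and repeat the summaries without flagged epochs as a sensitivity analysis.

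Cost: about one minute and one form per visit, some analyst time for flagging, and fewer usable minutes in the sensitivity analysis. No additional subjects or equipment are needed.

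### Read literally, the Ensemble Average step averages signals across channels before the spectral analysis, which removes location, can cancel band power, and leaves no quantity to set against the regional and coherence literature

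*Combined protocol and SAP*

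**What the plan says.** All references are to the combined protocol and SAP.

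- **Processing (B3.A, Study procedures, 1) EEG).** After down-sampling and band-pass filtering comes the Ensemble Average: "In this step, signal acquired from every selected channel would be averaged". The next sentence adds: "There are fifteen signals from the instruction that are averaged into one signal representing the instruction". The following step reads: "STFT will be used to determine a dominant frequency from the signal of an ensemble average result when the event occurs". The last reads: "ERD/ERS during event is calculated with the above data". The selected channels are neither listed nor counted, and the fifteen signals are not defined.
- **Aim (end of B2).** "This study will investigate if Isha Kriya produces EEG changes comparable to that of established literature".
- **Literature (B2, Meditation and current literature; Network integration).** The protocol reports from its sources that "meditation produces different activities at different locations such as increased alpha activity in frontal regions", and adds posterior regions. It also reports that "EEG signals are sensitive to meditation using coherence and synchrony techniques as well as spectral analysis", and that "meditation is associated with increased brain network integration". It further cites findings given without a location, such as higher alpha and theta in meditators.
- **Analysis and endpoints (B3.B).** The declared targets are alpha versus beta, waveform differences between novices and experienced meditators and over the 6 weeks, ERP amplitude and latency, power spectral density and time-frequency oscillations. None names an electrode site, a region, or a coherence or network measure.

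**The concern.** Two things are at stake.

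First, part of the literature named as comparator is stated by region or between channels. A single averaged trace has no region, and coherence needs at least two signals. If Isha Kriya changed frontal alpha only, the described output could not show where the change arose. An unremarkable result could then be taken as a lack of agreement with the literature, when the matching quantity had not been computed.

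Second, the order of the steps matters even for what the plan does promise. Raw signals are averaged first and spectra are taken afterwards. The power of an averaged signal depends on the phase relation between channels as well as on the power in each. A difference in synchrony between novices and experienced meditators, or between baseline and 6 weeks, could therefore appear as a difference in power. If cancellation differs between bands, the alpha-versus-beta description is affected too.

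**Working it through.** The plan gives no figure on this point, so there is none to reproduce. The check asks what averaging signals does to band power.

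**Inputs.** The sampling rate of 500 S/s is from B3.A. The rest are assumptions: 32 channels (suggested by the device name), 16 labelled frontal and 16 posterior, one 8–12 Hz source of unit power per region, white noise with SD 0.5, and a 300 s recording.

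**Formula.** Let the two regions have alpha power P_F and P_P and correlation r. With equal channel counts and noise ignored, the power of the average is

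(P_F + P_P + 2r√(P_F·P_P)) / 4.

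**Step 1: same channel power, different phase relation (P_F = P_P = 1).**

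| Regions | Formula | Simulated mean channel power | Simulated power of averaged signal | Simulated coherence, one frontal and one posterior channel |
|---|---|---|---|---|
| In phase (r = 1) | (1+1+2)/4 = 1.00 | 0.99 | 0.99 | 0.99 |
| Independent (r = 0) | (1+1+0)/4 = 0.50 | 0.98 | 0.49 | 0.01 |
| Antiphase (r = −1) | (1+1−2)/4 = 0.00 | 0.99 | 0.00 | 0.99 |

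Channel power is essentially constant down the table, yet the averaged signal's power runs from 0.99 to 0.00. The first and last rows have the same coherence and opposite extremes of averaged power, so the averaged power does not stand in for coherence either.

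**Step 2: same size of change, different place (independent regions).**

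- Frontal alpha power doubled: (2+1)/4 = 0.75 by formula; 0.731 simulated.
- Posterior alpha power doubled: (1+2)/4 = 0.75 by formula; 0.728 simulated.

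The two cases cannot be told apart in the averaged signal.

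**Step 3: regions kept separate.** In the same simulation, doubled frontal alpha gives 1.97 frontal and 0.98 posterior. Doubled posterior alpha gives 0.99 frontal and 1.95 posterior. The place of the change is recovered.

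**Step 4: the other reading.** If the fifteen signals are repetitions averaged within each channel, none of the losses in Steps 1 and 2 arises. What remains is that B3.B specifies no regional or between-channel measure, so the choice of sites would be made after the data are seen.

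**The case against.** The strongest reply is that the premise is only one reading. Averaging repetitions is a natural sense of the term ensemble average, and the fifteen signals are said to come from the instruction. This stands as a real ambiguity. It does not settle the matter. The sentence before it speaks of channels, and the meditation described in B3.A (7 minutes of breathing, seven vocalised sounds, 5 minutes of sitting) contains no instruction stated to be repeated fifteen times.

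Three stronger readings are tempting, and the documents do not support them.

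- *The whole 32-channel recording is collapsed into one head-wide signal.* The text refers to selected channels, which need not cover the head.
- *The study sets out to make frontal, posterior, coherence and network comparisons and cannot make them.* The aim is a general comparison with the literature. The regional, coherence and network findings are background, and no endpoint names them. The coherence citation itself also mentions spectral analysis. Averaging is an analysis step, B3.A says device data are stored, and outside collaborators will assist with the EEG analysis. Channel-level work is therefore not ruled out; it is not described.
- *The loss is a simple dilution of a known percentage.* For example, a 50% rise in 5 of 15 channels of equal power gives 1 + (5/15)(0.5) = 1.167. That averages power on assumed inputs. The text averages signals, where the result depends on phase, so such a figure does not describe this step.

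It is also fair that this is a descriptive pilot with no rule equating a null result with disagreement with the literature. The risk is one of interpretation.

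**Conclusion.** The point holds in a limited form. On the literal, across-channel reading, the only processing chain in the documents gives a result without location or between-channel information, and its band power can fall anywhere between full value and zero according to phase. The plan as described then supplies no quantity to match the regional and coherence findings within its stated comparison. Global spectral comparisons remain open, with possible distortion. On the within-channel reading, the shortfall is narrower: location is kept but no regional measure is fixed.

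The figures of 0.99, 0.49 and 0.00 come from two idealised regions with assumed equal power. They show the range of the mechanism and do not estimate what this trial's recordings would show. Real channels would probably fall between the extremes. No sample size, power or significance level is affected.

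**What to change.** 1. Reword the Ensemble Average step so that any averaging is over repetitions within a channel, never across channels. Define the fifteen signals and list the selected channels.
2. Compute power spectral density, time-frequency measures and ERD/ERS per channel.
3. Summarise band power in one frontal and one posterior electrode group, both listed before the data are seen. Average power within each group, not raw signals. Report by novice or experienced group and by visit, descriptively. Show the all-channel summary as an additional display.
4. If the comparison with the coherence literature is kept, add one fronto-posterior coherence value per band. If it is not, limit the stated literature comparison to spectral measures. One coherence value would not by itself address the network-integration finding.

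The change needs some wording and a modest amount of extra analysis on recordings already planned. Its drawback is a few more descriptive numbers in about 10 completers, which should be presented as description and not tested.

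### Dominant frequency and ERD/ERS are computed from a waveform average, which suppresses activity that is not phase-aligned; power should be computed per channel and epoch first and averaged afterwards

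*Combined protocol and SAP*

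**What the plan says.** Section B3.A, under EEG, introduces the processing with "EEG measures brain waves by the following processes" and then gives a single sequence: down-sampling, band-pass filtering, ensemble average, short-time Fourier transform (STFT), and event-related desynchronisation/synchronisation (ERD/ERS).

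The averaging step opens with "In this step, signal acquired from every selected channel would be averaged" and continues "There are fifteen signals from the instruction that are averaged into one signal representing the instruction". The first sentence points to channels. The second could equally mean repeats of an instruction. The STFT step reads "STFT will be used to determine a dominant frequency from the signal of an ensemble average result when the event occurs", and the last step reads "ERD/ERS during event is calculated with the above data".

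Section B3.B gives a two-part primary endpoint: event-related potential amplitude and latency, and spectral density with time-frequency oscillations. It names alpha against beta as the change of interest. It lists neither dominant frequency nor ERD/ERS as an endpoint.

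**The concern.** Averaging waveforms keeps what is aligned in phase across the averaged signals and cancels the rest. That is the right operation for event-related potential amplitude and latency. ERD/ERS and band power are meant to capture rhythms whether or not they are phase-locked, so for them the order of operations matters: power has to be taken before averaging.

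Three things are at stake.
- **Precision.** What is left of the rhythm after averaging is a small and erratic remainder.
- **Bias in ERD/ERS and dominant frequency.** Any phase-locked component is kept whole while the rest shrinks, so it counts for far more than its share.
- **Comparability.** If phase-locking differs between visits or between novices and experienced participants, averaged power differs even when true power does not. On the meditation itself, section B3.A says "The subjects can utilize the online-guided meditation or follow the instructions on their own", and the plan does not say which applies during the EEGs. Equal locking therefore cannot be taken for granted.

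If the averaged signals are channels, scalp location is also lost, although section B2 cites alpha effects specific to frontal and posterior regions.

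**Working it through.** The plan states no figure for this point, so there is none to reproduce. The only input it supplies is N = 15 averaged signals. It gives no averaging unit, epoch length, event, reference window or degree of phase-locking. All values of these below are assumptions.

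**1. Power kept, repeats reading.** Let r be the phase-locked share of power, which is the square of the usual phase-locking value. Power kept after averaging = r + (1 - r)/15 = (1 + 14r)/15.
- r = 0: 1/15 = 6.7%
- r = 0.02: 1.28/15 = 8.5%
- r = 0.05: 1.70/15 = 11.3%
- r = 0.10: 2.40/15 = 16.0%

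**2. False change between recordings or groups, repeats reading.** With true power constant and r rising from 0, the apparent change is 10 log10(1 + 14r). This is +1.1, +2.3 and +3.8 dB for r = 0.02, 0.05 and 0.10 (phase-locking values of about 0.14, 0.22 and 0.32). If r is the same in both recordings, the factor cancels. In simulation a true +3.0 dB was kept at +2.8 to +2.9 dB averaging first, against +2.9 dB taking power first.

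**3. ERD/ERS level, repeats reading.** Let d be the true proportional fall in the non-locked rhythm, and q the in-band locked power during the event as a share of reference power. As ratios of expected power:
- averaging first: [(1 - d)/15 + q]/(1/15) - 1 = -d + 15q
- power first: (1 - d) + q - 1 = -d + q

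For d = 50%:

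| q | averaging first | power first |
|---|---|---|
| 0 | -50% | -50% |
| 1% | -35% | -49% |
| 3.3% | 0% | -47% |
| 5% | +25% | -45% |

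The sign reverses once q exceeds d/15: 3.3% for d = 50%, and 2% for d = 30%.

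**4. ERD/ERS noise with no locked part, repeats reading.** Assume a fluctuating Gaussian rhythm, one spectral estimate per window and d = 50%. The event-to-reference ratio is 0.5 × F(2,2) averaging first and 0.5 × F(30,30) power first. The sign is wrong when F > 2, with probability 1/(1 + 2) = 33% against 3%. A simulation with constant-amplitude oscillations plus noise gave 33% against 0%. Longer windows, which hold several independent estimates, reduce these error rates.

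**5. Group-level precision, repeats reading.** Simulation with a 10 Hz rhythm of 0.3 to 2 Hz linewidth gave a within-subject SD of the change 3.7 to 4.1 times larger averaging first (theory: √15 = 3.9). The inflation of the group standard error is √[(T² + SDavg²)/(T² + SDpow²)] - 1, where T is an assumed between-subject SD.
- 4 s epochs, T = 1 dB: SDs of 1.80 to 3.25 dB against 0.46 to 0.88 dB, so 87% to 155%.
- 48 s epochs, T = 3 dB: SDs of 0.45 to 0.88 dB against 0.12 to 0.24 dB, so 1% to 4%.

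**6. Dominant frequency, repeats reading.** With a fluctuating 10 Hz rhythm and no locked tone, the peak stayed in alpha in at least 99.9% of runs either way. A locked 5 Hz tone with 5% of alpha power, lasting the whole epoch, became the peak in 60% to 100% of averaging-first runs and 0% of power-first runs.

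**7. Channels reading.** Power kept is the squared modulus of the mean of exp(i × phase). For 15 phases evenly spaced with endpoints included, over 0, 90, 180, 270 and 360 degrees, it is 100%, 79%, 35%, 5% and 0.4%. Steps 1 to 6 do not carry over to this reading.

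**The case against.** The strongest reply has five parts.

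- **The affected outputs are not endpoints.** Correct: section B3.B names neither. A reader might infer that the whole oscillation endpoint is computed from the averaged trace and is therefore invalid. The text does not say so, because only dominant frequency and ERD/ERS are tied to the average. What remains is that no unaveraged analysis is described. The real-time spectrogram mentioned in B3.A is a device feature, and the outside collaborators' role in B3.B comes with no method, so neither supplies one.
- **Most of the sizes assume repeats, while the step's first sentence says channels.** Correct. The unit is unsettled, and the meditation script does not explain the count of fifteen: its only counted element is a "sound seven times; sitting for 5 minutes with eyes closed". On the channels reading the loss runs from none to nearly all.
- **The bias is hypothetical.** Correct in part. A reader might infer that averaging always distorts ERD/ERS or will reverse its sign. It does not: with no locked component the expected level is preserved and only the noise grows. No value of q or r comes from the documents.
- **ERD/ERS cannot be run as written in either order, because no event or reference window is defined.** This stands, and the fix has to cover it.
- **This is a descriptive pilot with no EEG hypothesis test named.** This limits the consequences. But the EEG measures are the study's main output, and a displaced peak or wrong-sign ERD would misdescribe them.

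**Conclusion.** The concern holds for the two outputs that the text ties to the averaged signal. It is explicit for dominant frequency and the natural reading for ERD/ERS, since no other input is named. For the spectral part of the primary endpoint it is an open question rather than an established error.

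On the repeats reading, 6.7% of random-phase power survives. ERD/ERS becomes -d + 15q where it should be -d + q. A shift in the locked share of power from 0 to between 0.02 and 0.10 produces a false +1.1 to +3.8 dB. On the channels reading, between 100% and 0.4% of power survives over the phase spreads examined, and scalp location is lost. The bias figures require a phase-locked component, which the documents neither show nor rule out. The loss of group precision runs from negligible to large, depending on assumed epoch length and between-subject spread.

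The method is worth correcting before analysis, because the stated order has no advantage for power measures and the study plans on as few as 10 completers.

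**What to change.** Amend the processing steps in B3.A as follows.
1. For dominant frequency, ERD/ERS and the oscillation endpoint, compute STFT or Welch power per channel and per epoch (or fixed window), then average the power.
2. Keep the ensemble average, taken over repeats within a channel, for event-related potential amplitude and latency only. State what the fifteen signals are.
3. Define the event and the reference segment for ERD/ERS. If the recordings hold no event markers or reference segment, report band power in fixed windows instead, for example separately for the breathing and the silent sitting phases.

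If the sponsor already intends to take spectral density from unaveraged data, one sentence settles that part. The dominant-frequency and ERD/ERS wording still needs changing.

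The cost is wording and a little more analysis, assuming unaveraged channel data are kept. The storage sentence, "These data are stored in microSD offline in Holter mode", directly follows the mention of accelerometer data and need not cover the EEG, so retention should be stated explicitly. Event-based ERD/ERS may not be recoverable from recordings made without markers.
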